3.5.7.2 Weekly Assessments

The following information will be entered into the eDiary once each week during an entry of the evening diary (see Appendix 3):

• Degree of relief assessment

The following items are assessed on a 7-point balanced ordinal scale: 1=Significantly relieved, 2=Moderately relieved, 3=Somewhat relieved, 4=Unchanged, 5=Somewhat worse, 6=Moderately worse, 7=Significantly worse

How would you rate your heartburn (a pain or burning sensation in your chest, behind the breastbone) over the past 7 days?

How would you rate your regurgitation (the feeling of stomach contents, either liquid or food, moving upwards to your throat or mouth) over the past 7 days?

How would you rate your overall GERD symptoms over the past 7 days?

Compared to before you started this study, how would you rate your heartburn (a pain or burning sensation in your chest, behind the breastbone) over the past 7 days?

Compared to before you started this study, how would you rate your regurgitation (the feeling of stomach contents, either liquid or food, moving upwards to your throat or mouth) over the past 7 days?

Compared to before you started this study, how would you rate your overall GERD symptoms over the past 7 days?

Bothersomeness Assessment.

The following items are assessed on a 5-point ordinal scale: 1=Not at all, 2=A little bit, 3=A moderate amount, 4=A great deal, 5=An extreme amount

How much were you bothered by heartburn (a pain or burning sensation in your chest, behind the breastbone) over the past 7 days?

How much were you bothered by regurgitation (the feeling of stomach contents, either liquid or food, moving upwards to your throat or mouth) over the past 7 days?

How much were you bothered by your overall GERD symptoms over the past 7 days?

• Treatment Satisfaction Assessment

The following items are assessed on a 5-point ordinal scale: 1=Very dissatisfied, 2=Dissatisfied, 3=Neither satisfied nor dissatisfied, 4=Satisfied, 5=Very satisfied

How would you rate your satisfaction with the study treatment?

3.5.7.3 Study Visit Assessments

The following assessments will be performed at the study visits indicated:

• WPAI-Sleep Disturbance-GERD

The Work Productivity and Activity Impairment Questionnaire: Sleep Disturbance-GERD (WPAI-Sleep-GERD) includes questions about time lost from work, reduced productivity while at work, and reduced productivity while doing regular daily activities resulting from sleep disturbance due to GERD symptoms. Patients will complete the WPAI-Sleep-GERD at the Randomization Visit, the Week 4 Visit, and at the EOT Visit and will record their responses in the eDiary.

• EQ-5D-3L

The EuroQol (EQ)-5D-3L is a generic measure of health widely used in Europe.(13) The first component consists of 5 questions assessing the following dimensions: mobility, self-care, usual activities, pain/discomfort, and anxiety/depression. Responses to the 5 questions define a health state for which a utility index can be derived from published algorithms.(14) The

second component of the EQ-5D is a visual analogue scale, asking patients to rate their health from 0 to 100 (0 represents worst imaginable health state and 100 represents best imaginable health state). Patients will complete the EQ-5D-3L at the Randomization Visit, the Week 4 Visit, and at the EOT Visit and will record their responses in the eDiary.

3.5.8 Other Assessments

3.5.8.1 Esophagogastroduodenoscopy

All patients will be required to undergo an EGD during the Screening Period. There should be a minimum of 7 days between the EGD and the start of the Pretreatment Period to allow for pH testing and patient stabilization. EGDs will be interpreted by the local site personnel and by a central reader. Details are provided in a separate study manual (Image Acquisition Guidelines for Ironwood Pharmaceuticals, Inc. Protocols C3718-301/C3718-302; WorldCare Clinical).

An EGD will be performed at the Week 8 / EOT Visit in all patients who completed at least 4 weeks of treatment and had erosive esophagitis on the EGD obtained during the Screening Period (based on the Los Angeles [LA] classification of esophagitis [Appendix 5], as determined by either the site personnel or the central reader).

3.5.8.2 **Bravo**TM

At all sites, all patients will undergo up to 96 hours of pH testing with the Bravo device. If for some reason 96 hours of testing is not possible, then approximately 48 hours of testing is acceptable. All patients will return to the site with their Bravo pH monitor after approximately 96 hours (or 48 hours where applicable) to return the recording device. To determine eligibility, a centralized review of pH monitoring will be conducted for each patient. Please refer to the Bravo Site Manual for specific instructions.

3.6 SCHEDULE OF EVENTS

The schedule of study procedures and assessments is presented by visit in the Schedule of Evaluations within the Protocol Synopsis. Procedures and assessments by study visit are provided in the following sections.

3.6.1 Screening Period (Day -49 to Day -15)

3.6.1.1 Screening Visit (Visit 1) Procedures

- Review of inclusion and exclusion criteria
- Signing of ICF
- Register visit in IWRS
- Demographics
- Medical and disease history
- Physical examination
- Body weight and height
- Begin H2RA and antacid washout (for 5 days before the EGD and Bravo pH monitoring [H2RA] and 1 calendar day before the EGD and Bravo pH monitoring [antacids])
- EGD (see Section 3.5.8.1)
- Up to 96 hours of pH testing with a Bravo device (if 96 hours of testing is not possible, then approximately 48 hours of testing is acceptable)
- Seated vital signs
- 12-lead ECG
- Prior medications (all medicines taken during the 30 days before the Screening Visit, most recent use of an H2RA, antacid, and PPI)
- Collection of blood and urine samples for clinical laboratory test, including:

Clinical chemistry

Hematology (complete blood count [CBC])

Coagulation

Urinalysis

- Pregnancy test for all female patients of childbearing potential (must be confirmed negative; positive urine test results will be confirmed via serum pregnancy test)
- Drug and alcohol screening, including a urine drug screen for selected drugs of abuse (cocaine, barbiturates, amphetamines, opiates, benzodiazepines, cannabinoids, and phencyclidine) and a serum alcohol screen
- AE evaluation (throughout the Screening Period)

3.6.1.2 Pretreatment Visit (Visit 2) Procedures

- Register visit in IWRS
- Review of inclusion and exclusion criteria
- Body weight
- Prior and concomitant medications and procedures
- AE evaluation (throughout the Pretreatment Period)
- Liquid antacid rescue medicine dispensation
- eDiary training and dispensation (for recording daily and weekly evaluations throughout the Pretreatment and Treatment Periods)

3.6.2 Treatment Period (Day 1 to Day 57)

For all visits during the Treatment Period, patients will take their PPI and study medication (except for the Randomization Visit) prior to reporting to the study site.

3.6.2.1 Randomization Visit (Visit 3) Procedures

- Register visit in IWRS
- Review of inclusion and exclusion criteria
- Body weight
- Seated vital signs
- 12-lead ECG
- Concomitant medications and procedures
- Collection of blood and urine samples for clinical laboratory tests, including:

Clinical chemistry

Hematology (CBC)

Coagulation

Urinalysis

- Pregnancy test for all female patients of childbearing potential (must be confirmed negative; positive urine test results will be confirmed via serum pregnancy test)
- AE evaluation (throughout the Treatment Period)

- Liquid antacid rescue medicine dispensation (if needed)
- Review eDiary
- WPAI-Sleep Disturbance-GERD
- EQ-5D-3L
- Randomization
- Study medication dispensed
- Study medication administration (first dose of study medication taken in clinic with liquid and a snack. Patients should take their second dose that evening, with liquid, immediately upon completion of dinner and ensure that at least 8 hours have elapsed since the first dose in clinic).

3.6.2.2 Week 4 (Visit 4) Procedures

- Register visit in IWRS
- Body weight
- Seated vital signs
- Concomitant medications and procedures
- Collection of blood and urine samples for clinical laboratory tests, including:

Clinical chemistry

Hematology (CBC)

Coagulation

Urinalysis

- Pregnancy test for all female patients of childbearing potential (must be confirmed negative; positive urine test results will be confirmed via serum pregnancy test)
- AE evaluation (throughout the Treatment Period)
- Liquid antacid rescue medicine dispensation (if needed)
- Review eDiary
- WPAI-Sleep Disturbance-GERD
- EQ-5D-3L
- Study medication dispensed
- Return of all unused study medication

3.6.2.3 Week 8/End-of-treatment (Visit 5) Procedures

- Register visit in IWRS
- Physical examination
- Body weight
- EGD (A repeat EGD will be performed at the Week 8 / EOT Visit for all patients who have completed at least 4 weeks of treatment and had erosive esophagitis on the screening EGD [based on the LA classification of esophagitis, see Appendix 5] as determined by either the site personnel or the central reader; see Section 3.5.8.1)
- Seated vital signs
- 12-lead ECG
- Concomitant medications and procedures
- Collection of blood and urine samples for clinical laboratory tests, including:

Clinical chemistry

Hematology (CBC)

Coagulation

Urinalysis

- Pregnancy test for all female patients of childbearing potential (must be confirmed negative; positive urine test results will be confirmed via serum pregnancy test)
- AE evaluation (throughout the Treatment Period)
- Review eDiary
- WPAI-Sleep Disturbance-GERD
- EQ-5D-3L
- Return of all unused study medication
- Return eDiary

3.6.3 Follow-up Phone Call

The study site will contact all patients via telephone 7 days following the EOT Visit to collect information regarding ongoing AEs/SAEs/concomitant medications and any new AEs/SAEs/concomitant medications and procedures since the EOT Visit (Section 3.6.2.3). This information will be recorded via EDC.

3.6.4 Early Termination Procedures

Patients who discontinue from the study for any reason should complete the assessments required at the EOT Visit (Section 3.6.2.3) at the time of their discontinuation.

3.7 STATISTICAL METHODS

Statistical analysis methods are summarized in the following sections. Additional details regarding the statistical methods will be provided in the Statistical Analysis Plan (SAP), to be finalized prior to unblinding of the study.

3.7.1 Analysis Populations

Screened Population consists of all patients who signed informed consent and received a patient identification (PID) number.

Randomized Population consists of all patients who were assigned to a treatment group (placebo or IW-3718) via randomization.

Safety Population consists of all randomized patients who received at least 1 dose of study drug.

Modified Intent-to-Treat (mITT) Population consists of all randomized patients who received at least 1 dose of study drug and had at least 1 postbaseline primary efficacy assessment.

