A total of 282 patient were randomized. The modified ITT Population included 280 patients (68-71 patients per treatment arm), approximately half (52%) of whom had EGD confirmation of erosive esophagitis (EE) at baseline (52%). Demographics and baseline characteristics were generally similar across the treatment groups. For the primary endpoint, dose-dependent improvements were observed in Week-8 heartburn severity scores; percent changes from baseline were -46.0, -49.0, -55.1, and -58.0 for the placebo, IW-3718 500 mg, 1000 mg, and 1500 mg treatment groups, respectively (dose-response test nominal p-value = 0.02). The treatment difference for the IW-3718 1500 mg group compared with placebo was -11.9 (nominal p-value = 0.04). Week-8 percent change from baseline in regurgitation frequency score was significantly better for the IW-3718 1500 mg group (-55.4) compared with placebo (-37.9) (difference -17.5; nominal p-value = 0.01). Numerical gains were seen at each week of treatment starting at Week 2 for heartburn severity for the IW-3718 1500 mg group versus placebo. Greater weekly improvements were seen at this dose in EE patients. Overall responder rates for heartburn and regurgitation were 52.9% and 46.3% for the IW-3718 1500 mg group compared with 37.1% and 34.3% for the placebo group, respectively; greater improvements compared with placebo were seen in EE patients (Table 1). Note that although a 30% reduction was defined in the protocol as being the criterion for a weekly improvement in WHSS and WRFS, pre- and post-hoc pooled anchor-based analyses suggested that a 45% reduction is better at defining a clinically significant response to treatment.

Table 1. Overall Heartburn and Regurgitation Responders (Study ICP-3718-202; Modified Intent-to-Treat Population)

	% Responders				_	
			IW-3718			
Parameter	Placebo w/ PPI	500 mg w/PPI	1000 mg w/PPI	1500 mg w/ PPI	Treatment Difference ¹	
Heartburn						
≥30% Responder						
All patients (N=280)	54.3	52.1	62.0	66.2	11.9	
EE patients (N=145)	47.2	50.0	59.5	69.4	22.2	
≥ 45% Responder						
All patients (N=280)	37.1	43.7	42.3	52.9	15.8	
EE patients (N=145)	30.6	41.7	32.4	50.0	19.4	
Regurgitation ²						
≥30% Responder						
All patients (N=277)	42.9	55.7	64.3	64.2	21.3	
EE patients (N=142)	36.1	54.3	58.3	62.9	26.7	
≥ 45% Responder						
All patients (N=277)	34.3	38.6	37.1	46.3	12.0	
EE patients (N=142)	27.8	40,0	27.8	42.9	15.1	

EE=erosive esophagitis; PPI=proton pump inhibitor

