6.3. Handling of Dropouts/Missing Data Imputation Method

The WHSS (Section 7.9.1.2) is the average of non-missing Daily Heartburn Severity Scores (DHSS) for the week (Appendix 1). If a patient who reported DHSS for fewer than 1 day during a week within the Treatment Period for a given week, then WHSS is missing for that week.

The WRFS (Section 7.9.2) for a week is the average of the non-missing Daily Regurgitation Frequency Scores (DRFS) for that week (Appendix 1). If a patient who reported DRFS for fewer than 1 day during a week within the Treatment Period for a week, then WRFS is missing for the week.

For responder parameters, OHR (Section 7.9.2), a patient who reported daily symptom severity scores for fewer than 4 days during a week within the Treatment Period will be considered a non-responder for that week. A patient will be deemed a weekly non-responder for all weeks following the patient's discontinuation from the study.

Unless stated otherwise, missing data will not be imputed for any of the efficacy parameters.

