7. ANALYSIS METHODS

7.1. Analysis Populations

- Screened Population consists of all patients who signed informed consent and received a patient identification (PID) number.
- **Randomized Population** consists of all patients who were assigned to a treatment group (placebo or IW-3718) via randomization.
- **Final Efficacy Analysis Randomized Population** consists of all patients who were randomized prior to or on August 4, 2020.
- **Safety Population** consists of all randomized patients who received at least 1 dose of study drug. Safety analysis will be based on the Safety Population, in which patients are evaluated according to the treatment they received.
- **Modified Intent-to-Treat (mITT) Population** consists of all patients who were randomized prior to or on August 4, 2020, and who received at least 1 dose of study drug and had at least 1 postbaseline primary efficacy assessment. This population will be used for the final efficacy analysis.
- Sensitivity Analysis (SA) Population consists of all randomized patients who received at least 1 dose of study drug and had at least 1 postbaseline primary efficacy assessment. This population will be used for the efficacy sensitivity analysis at completion of the study.

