7.9. Efficacy Analysis

The final efficacy analysis will be based on the mITT, while the SA Population will be used for the sensitivity efficacy analysis, and the analyses will be conducted according to the treatment assigned. Baseline values for efficacy parameters are defined as:

- For change from baseline continuous parameter and derived dichotomized response variables, the baseline will be derived from the eDiary and/or eCRF data collected for the last week of the Pretreatment Period (or Week -1), specifically the period from 7 days prior to the day of randomization.
- A time dependent proportion efficacy parameter that is defined as days the event of interest occurs, divided by the number of diary entry days during the relevant period. Its baseline period is the last 14 days (Week -2 to Week -1) prior to day of randomization.

For the change from baseline and response variables, if data for Week -1 are not available, data for Week -2 (the second last week of the Pretreatment Period) will be used.

For responder parameters derived from daily eDiary assessments, a patient who missed 4 or more daily assessments an analysis week will be consider a missing for that week and will be defined as a non-responder for that week. For continuous efficacy parameters, the analysis value for an analysis period is defined as the average of the non-missing values during that period (Appendix 1). If a patient who reported assessments for fewer than 1 day during a week within the Treatment Period, the average is missing for that week. For efficacy parameters no further imputation will be performed (see Section 7.9.1.3 for sensitivity analyses employing multiple imputation [MI] methods). Any efficacy assessments measured after the last dose date will not be included for analysis.

All primary and secondary efficacy parameters are listed in Table 4 will be tested in the given order to protect the overall family wide alpha level at 5%. The mITT Population will be used for the final analysis for all efficacy parameters. The SA Population will be used for the efficacy sensitivity analysis that include selected efficacy parameters at completion of the study.

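### The mITT condition removes dosed patients with no post-baseline diary from the Overall Heartburn Responder test, although the SAP's own rule would score them as non-responders

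*Protocol*

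**What the plan says.** Protocol 3.7.1 defines the mITT as "all randomized patients who received at least 1 dose of study drug and had at least 1 postbaseline primary efficacy assessment". The operative definition in SAP 7.1 restricts it to patients randomised by the August 4, 2020 cut "who received at least 1 dose of study drug and had at least 1 postbaseline primary efficacy assessment". SAP 7.9 then states: "The mITT Population will be used for the final analysis for all efficacy parameters". That includes OHR, the third test in the fixed sequence (Protocol 3.7.4.4, SAP 6.6).

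For OHR the SAP also has a missing-equals-failure rule. Under SAP 6.3 a patient with scores on "fewer than 4 days during a week within the Treatment Period will be considered a non-responder for that week". For discontinuation it adds: "A patient will be deemed a weekly non-responder for all weeks following" the patient's leaving the study. SAP 7.9.2 repeats the 4-day rule and requires at least 4 responder weeks, one of them Week 7 or 8.

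SAP 7.1 defines two further sets that bear on this. The Sensitivity Analysis (SA) Population has no date cut; it "consists of all randomized patients who received at least 1 dose of study drug and had at least 1 postbaseline primary efficacy assessment", so it has the same diary condition. The Final Efficacy Analysis Randomized Population "consists of all patients who were randomized prior to or on August 4, 2020" and has neither a dosing nor a diary condition, but no stated analysis uses it.

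**The concern.** A condition that suits the MMRM has been carried over to an endpoint that does not need it. A patient with no post-baseline score contributes nothing to a model for change from baseline. For OHR the same patient has a fully determined outcome, non-responder, with nothing left to impute. The baseline strata for the CMH test are also known before dosing.

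Membership of the test population therefore depends on behaviour after randomisation. Of two patients who stop on Day 1 or 2 for the same reason, the one who made a single evening entry is a failure and the one who made none is left out. Everyone left out this way is a failure under the plan's own scoring, so the reported responder rate can only be too high in an arm with such losses. OHR is alpha-controlled and also opens the fourth test, so its denominator should follow its own rule.

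**Working it through.** **Inputs.**
- Planned OHR rates (Protocol 3.7.7, SAP Table 1): placebo p0 = 18/49 = 0.3673; IW-3718 p1 = 31/55 = 0.5636; difference 19.63 points.
- 330 per arm (Protocol 3.7.7). Variant: 550/2 = 275 per arm, because SAP 3.4 gives about 550 patients.
- Two-sided 0.05; chi-square for OHR.
- d, the share of dosed patients in an arm with no post-baseline diary: not given in the documents. Assumed range 0% to 5%.
- Proxy for d: Protocol 1.3 reports 282 randomised in Phase 2b and "The modified ITT Population included 280 patients", so (282 − 280)/282 = 0.71%.

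**1. The plan's own figure.** A two-proportion power calculation at 330 per arm gives 0.9992 for OHR alone. The two earlier steps give 0.9933 (WHSS: difference 0.43, SD √((1.20² + 1.29²)/2) = 1.246) and 0.9999 (WRFS: difference 0.45, SD √((1.12² + 0.91²)/2) = 1.020). Treated as independent, 0.9933 × 0.9999 × 0.9992 = 0.992. The stated 99% is reproduced and is not in dispute.

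**2. The rule applied to a patient with no diary.** Diary days in Weeks 1 to 8: 0 each week. Since 0 < 4, the patient is a non-responder in all 8 weeks. That is 0 responder weeks against the 4 required, so an OHR non-responder. The mITT condition removes the patient first.

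**3. Effect of counting these patients.** They add to the denominator only, so the rate in all dosed patients is q = p × (1 − d). The mITT overstates the difference by p1·d1 − p0·d0. Planned rates are taken as mITT rates:

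| d placebo | d active | placebo | IW-3718 | difference | power, 330 | power, 275 |
|---|---|---|---|---|---|---|
| 0 | 0 | 36.73% | 56.36% | 19.63 | 0.9992 | 0.9966 |
| 0.71% | 0.71% | 36.47% | 55.96% | 19.49 | 0.9991 | 0.9963 |
| 2% | 2% | 36.00% | 55.24% | 19.24 | 0.9989 | 0.9956 |
| 5% | 5% | 34.90% | 53.55% | 18.65 | 0.9982 | 0.9936 |
| 0 | 0.71% | 36.73% | 55.96% | 19.23 | 0.9989 | 0.9955 |
| 0 | 2% | 36.73% | 55.24% | 18.50 | 0.9979 | 0.9926 |
| 0 | 5% | 36.73% | 53.55% | 16.81 | 0.9921 | 0.9788 |

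At the proxy in both arms the difference moves by 19.63 − 19.49 = 0.14 point. As an extreme, 0.71% × 660 = 4.7, say 5 patients, all on IW-3718: 0.564 × 330 = 186.1 responders, and 186.1/325 = 57.3% instead of 56.4%, or 0.9 point.

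**4. Direction.** The exclusion favours IW-3718 when p1·d1 > p0·d0, that is, when d0/d1 < 0.5636/0.3673 = 1.53. With 0.7% lost on active and 1.0% on placebo, restoring them costs active 56.4% × 0.7% = 0.395 point and placebo 36.7% × 1.0% = 0.367 point, so active was favoured although placebo lost more. With 0.71% lost on placebo only, the mITT understates the difference by 36.73% × 0.71% = 0.26 point.

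**5. How close a result must be.** At planned rates, 96 active-only exclusions would be needed to lose significance (96/426 = 22.5% of the dosed active arm). At the boundary one is enough: 121/330 against 146/330 gives p = 0.047, and 121/330 against 146/331 gives p = 0.051.

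**The case against.** The strongest reply is that this is a prespecified, uniformly applied mITT and that the excluded group should be nearly empty. Eligibility requires diary entries on at least 5 days in each of the two weeks before treatment (inclusion criterion 10). The first dose is taken in clinic, and that evening's entry already counts, since Week 1 begins on Day 1. Only a patient who never completes one evening entry after dosing is lost. Counts by population and arm, and discontinuations by week, will be tabulated (Protocol 3.7.3, SAP 7.2), so an imbalance would be visible. Moving OHR to another set also splits a sequence that SAP 6.6 places in the mITT. All of this stands, and it limits the size of the point. It does not remove the mismatch between rule and population, and disposition tables do not change the alpha-controlled test.

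A reader might infer that the exclusion flatters IW-3718 because early intolerance is likelier there. Protocol 3.4.5 does report nausea in 8.8% at 1500 mg against 2.9% on placebo, but that is overall incidence, neither early nor linked to stopping. The closer figure, Phase 2b discontinuations due to TEAEs, is 3 on placebo and 3 on 1500 mg (Protocol 1.3). A reader might also infer that the arm with more early losses always gains; step 4 shows that it need not. Nor is 2 of 282 a measured rate of dosed patients without a diary. It is randomised minus mITT, may consist of undosed patients, and the Phase 2b mITT definition is not given.

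**Conclusion.** The inconsistency is real. The OHR test drops patients whom the plan's own rule calls failures, on the basis of something that happens after randomisation. Neither the SA Population nor the imputation analysis in SAP 7.9.1.3, which covers only the primary parameter, brings them back. 'Failure' here means failure under the scoring rule; the documents do not say why such a patient would have no diary.

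The expected effect is well under 1 point. This rests on the planned rates and on 0.7% as an upper proxy, which assumes that the Phase 2b mITT had a comparable condition. Across the assumed 0% to 5%, power for OHR alone stays at or above 0.992 with 330 per arm and 0.979 with 275, so planned power is not threatened. The documents do not support a bias towards IW-3718 as an expectation. The point has practical weight only if the OHR result is close or early loss is clearly unequal; 5% on active alone would move the difference by 19.63 − 16.81 = 2.8 points. It is worth correcting because correction is cheap.

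**What to change.** In SAP 7.1 and 7.9.2.1, and in Protocol 3.7.4.3, specify that the OHR CMH test is run on all randomised and dosed patients within the August 4, 2020 cut. If never-dosed patients are also meant to count as failures, use the Final Efficacy Analysis Randomized Population instead, and say so. State that patients with no post-baseline diary are non-responders under the existing 4-day rule. Reconcile SAP Table 6, which says that missing OHR data are not imputed, with that rule. Report the number of such patients by arm. Keep the mITT for the MMRM and heartburn-free-days analyses, where a patient without diary data has no value.

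The cost is a few lines of text and one population flag, to be settled before unblinding. Responder rates may fall by a fraction of a point, and the OHR denominator will differ from that of the other tests in the sequence, so SAP 6.6 needs a matching sentence.
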